Provide a brief description of the study design or data collection methodologies. Details regarding protocol specific research procedures will be discussed in a later section.

Design: A two-arm randomized trial.

Randomization:

- Eligible households with at least one child (reference child) in the BGCAA after-school program whose caregiver/parent (guardian) (reference caregiver) consents to participate in the study will be randomized to either the active intervention or the control (1:1 ratio). Randomization will be stratified by the family's SNAP beneficiary status as SNAP could affect uptake of treatment elements offered in the family support arm.

Blinding: Outcome assessors, principal investigator, and biostatistician are blinded to participant allocation. Participant and other staff are unblinded.

Study arms (19 weeks) (Figure 1):

Randomized arms

Children in both intervention and control arms participate in the BGCAA's after-school program with CATCH curriculum.

1. Across participating school sites, the whole BGCAA's after-school program runs for 3h, Mon-Fri for the school year. Children enrolled are expected to attend a minimum of 2x/week.
2. CATCH curriculum will be delivered as a component of the after-school program in blocks of 45-60 min, twice a week.
3. Children also participate in active recreational time (approx. 60 min, offered 1x/week at a minimum) which consists of a mixture of free play, structured physical activity games, and/or sports activities (including soccer, football, and basketball).

Intervention arm: BGCAA after-school program + Family support

1. Children participate in the BGCAA's after-school program with CATCH curriculum as described above.
2. The child's caregiver will receive the following:
 - Family tip sheets sent via mobile text at the start of the program and then every 3 weeks, to a total of 6 txt messages.
 - Weeks 1-4 (4 weeks):
 - i. Welcome package mailed to the family's residence approximately in the first week of the program.

- ii. Weekly: 1 box of produce
- iii. Recipes accompanying each box (sample recipe card attached to submission)
- iv. Bi-Weekly: Grocery store gift cards (2x \$20, to a total of \$40)
- Weeks 5-19 (total of 10 weeks over the 19-week study timeline):

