 - i. For five weeks, an optional online form (or “*goal sheet*”) will be sent to the parent/caregiver (5 sheets in total) with questions about trying new FV items to be completed within the next 7 days. As an incentive, a \$10 gift card will be sent the following week to those who complete it (a potential total of \$50).
 - ii. Week 11: \$20 Grocery store gift card. Based on disruptions due to the school year breaks, we will provide an extra \$20 gift card to re-engage the week after a school holiday.

Control arm: BGC after-school program only

1. Children participate in the BGCAs after-school program with CATCH curriculum as described above.
2. At the end of the study, they will receive \$120 as grocery store gift cards.

[figure not shown]

Figure 1. Study design: 2 randomized arms

Outcomes:

- Primary:
 - Child's diet quality: measured by Healthy Eating Index, HEI, scores calculated from the Texas School Physical Activity and Nutrition (SPAN), 2nd Grade.
 - Child's fruits and vegetable consumption, measured by SPAN, 2nd Grade.
- Secondary outcomes:
 - Caregiver/parent diet quality, measured by HEI scores calculated from the SPAN, 8th Grade.
 - Child's physical activity levels
 - Child's body mass index, as percentile of BMI-for-age

Study measurements:

Timepoint measurements for all study participants (child-parent dyads) include:

- baseline (approximately up to 4 weeks prior to the first produce bag and grocery store gift card being distributed). Height and weight will be taken during the first 1-2 weeks of the research program start date during a BGCAA field day.
- mid-point (planned for approximately weeks 5-8)
- end-point (approximately between weeks 16 and 21). Height and weight will be taken during the 19th week of the program at the BGCAA's field day.

Outcomes	Tool	Time points	Administration
Child's Diet (primary)	TX SPAN 2 nd grade 2019-2020 – Dietary questions	Baseline, Mid-point, End point	Child, Guardian-reported Structured interview over the phone by RA
	SPAN Healthy Eating Index scores (includes total, healthy, and unhealthy scores)	Baseline, Mid-point, End point	Child, calculated from SPAN
Physical Activity	TX SPAN 2 nd grade 2019-2020 – Physical activity questions	Baseline, End point	Child, guardian-reported Structured interview over the phone by RA
	Physical Activity Questionnaire – Children		

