- Although the study team and our BGCAA partners are taking every effort to minimize the possibility, psychological distress related to in-person weight measurement could occur.
- Potential discomfort answering the research questions about diet and exercise habits, and other personal details about their lives and health.
- May discover new food allergies or sensitivities from trying new foods (intervention arm ONLY, control does NOT get food of any kind from us as part of the study).

32 Describe how each risk is mitigated/minimized.

To input text, click in the light grey area below. Note: Risks mitigation should be outlined in the consent form(s), as applicable.

- Participant study numbers within REDCap will be used to protect patient confidentiality. All data will be stored in either Box or REDCap.
- The height and weight measurements will be integrated within an activity at the health fair to minimize psychological distress related to these.
- The research staff does not have control of the contents in the produce boxes, and we will not be able to accommodate special diets or prevent potential allergens from being in a produce box. As such, having a food allergy related to any produce product will result in exclusion from the program.
- Resources will be provided to help families identify the signs of a food allergy or sensitivity (Intervention only). These resources will provide guidance on symptoms and what to do if symptoms appear, and will be given to intervention participants along with the recipes they receive with their produce boxes.

33 Data Safety Monitoring

For additional information regarding data safety monitoring boards and data safety monitoring plans, please see Section 21 of our [Policies and Procedures](#).

One of the following must be checked (A, B, or C).

A

In the investigator's opinion, this study is minimal risk and does not require a Data Safety Monitoring Plan (DSMP) or a Data Safety Monitoring Board (DMSB).

PLEASE NOTE: The IRB may determine minimal risk studies do require data safety monitoring under certain circumstances (e.g., if there is a known risk with an expected frequency).

B **This study does not have a Data Safety Monitoring Board, but researchers have an internal plan to monitor for safety (Data Safety Monitoring Plan (DSMP)).**

Complete Data Safety Monitoring Details

C **This study has a Data Safety Monitoring Board (DSMB).**

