Complete Data Safety Monitoring Details section below or upload this study's Data Safety Monitoring Board's charter that contains the information below.

34

Data Safety Monitoring (Details)

Complete this section if the study has a Data Safety Monitoring Plan. SKIP this section there is not a DSMP/DSMB.

If the study has a DSMB, ensure all items below are addressed in the charter (and charted uploaded to UTRMS-IRB) or provide additional information below, as needed.

A **How is safety information collected?**

To input text, click in the light grey area below.

B **When will safety data collection start (for each participant or for the whole study, as applicable)?**

To input text, click in the light grey area below.

C **How frequently will safety data be collected?**

To input text, click in the light grey area below.

D **Who will review the data for safety?**

To input text, click in the light grey area below.

E **How frequently will data be monitored for safety concerns?**

To input text, click in the light grey area below.

F What data will be reviewed?

To input text, click in the light grey area below.

G State the frequency or periodicity of the review of cumulative data.

To input text, click in the light grey area below.

H State any conditions that would trigger an immediate suspension of the research.

To input text, click in the light grey area below.

35

Early Withdrawal

Only complete this section if there are planned conditions under which a participant will be withdrawn from the study. If not applicable, skip to next section. Include this information in your consent form.

A List the criteria for withdrawing individual participants from the study (e.g., safety or toxicity concerns, emotional distress, inability to comply with the protocol, or requirements from study sponsor).

To input text, click in the light grey area below.

Participants may be withdrawn if it is determined it is unsafe for them to continue with the program. They may also be removed if a child leaves the BGCAA program and is in one of the randomized arms.

B Describe any necessary procedures for ensuring the safety of a participant who has withdrawn early.

To input text, click in the light grey area below.

There are no procedures in place to ensure the safety of a participant that is withdrawn early. This is a minimal risk study and being withdrawn poses no risk to the participant.

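### After randomization the protocol describes no scheduled question about food reactions, so any count of the one physical risk it names rests on unsolicited reports

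*Combined protocol and SAP*

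**What the plan says.** Section 31 gives four risks. Three concern confidentiality, distress over weighing, and discomfort with questions. The fourth is physical and belongs to one arm: "May discover new food allergies or sensitivities from trying new foods (intervention arm ONLY".

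The exposure is set out in section 4 and again in section 11. In "Weeks 1-4 (4 weeks" the family receives "Weekly: 1 box of produce". Families cannot choose the contents (section 11), and section 32 says that research staff do not control them either.

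The protocol describes two safeguards. Known produce allergy or restriction is an exclusion (section 13e), and the screening call in section 17 asks more widely about food allergies and sensitivities. Section 32 adds resources on recognizing symptoms and responding to them, which "will be given to intervention participants along with the recipes they receive with their produce boxes". The mailed welcome package also contains food allergy information (section 11).

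On stopping, section 35 states: "Participants may be withdrawn if it is determined it is unsafe for them to continue with the program". It does not say how the study learns of a problem or who decides.

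Three data collections are scheduled. The first is before the first box. The second is "mid-point (planned for approximately weeks 5-8". The third is at about weeks 16 to 21. Optional goal sheets go out at the start of weeks 5, 7, 9, 12 and 14. The outcome assessors and the principal investigator are blinded (section 4). Unblinded staff check the goal sheets (section 11).

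**The concern.** The protocol treats produce allergy as decisive at entry: it asks, and a positive answer keeps the family out. Once boxes of uncontrolled content are being handed out, no described procedure asks again. A reaction to an early box becomes known to the study only if the family volunteers it.

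Two things are at stake. The first is that the existing withdrawal criterion has no stated source of information. An unsolicited report might also reach a blinded interviewer or the blinded principal investigator and reveal the arm. The second is the harms record. A trial that does not ask cannot tell an absence of reactions from an absence of reports, and this is the only physical harm that the protocol anticipates in children aged about 6 to 11.

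**Working it through.** The protocol gives no figure on this point to reproduce. The check has three parts.

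**1. Timeline.** Inputs: box *k* is delivered in week *k*, for *k* = 1 to 4 (sections 4 and 11). The first goal sheet goes out at the start of week 5 (section 11). The mid-point interview falls at about weeks 5 to 8 (section 4). Gap to the goal sheet = 5 − *k*. Gap to the interview = (5 − *k*) to (8 − *k*). Boxes still due = 4 − *k*.

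| Box | Weeks to first goal sheet | Weeks to mid-point interview | Boxes still due |
|---|---|---|---|
| 1 | 4 | 4 to 7 | 3 |
| 2 | 3 | 3 to 6 | 2 |
| 3 | 2 | 2 to 5 | 1 |
| 4 | 1 | 1 to 4 | 0 |

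No scheduled question of any kind falls within the four box weeks. After a reaction to box 1, three more boxes are due before any form or interview reaches the family.

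**2. Content of the later contacts.** The instruments tabulated in section 4 cover diet (SPAN and the NHANES screener), physical activity, sedentary behavior, the SDQ, the SF-12, and height and weight. None is described as asking about reactions. The goal sheets are described in two ways. Section 4 has them sent "with questions about trying new FV items to be completed within the next 7 days", whereas section 11 says the questions concern produce the family has already been given. Neither description mentions a reaction. The number of described reaction questions after randomization is therefore zero over the whole study, not only in weeks 1 to 4.

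**3. What asking would buy.** If *n* children are each actively asked about and none has a reaction, the exact one-sided 95% upper bound on the per-child rate is 1 − 0.05^(1/*n*). Section 15 gives 75 per arm in the lowest enrollment scenario and about 140 as the target.

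- *n* = 75: 1 − 0.05^(1/75) = 0.039, or 3.9% (4 × 75 = 300 boxes).
- *n* = 140: 1 − 0.05^(1/140) = 0.021, or 2.1% (4 × 140 = 560 boxes).

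Here *n* is the number of families that answer. If only 64 did, the bound would be 1 − 0.05^(1/64) = 0.046, or 4.6%. Without active questioning, *n* is unknown and a zero count gives no bound. The documents give no reaction rate, so no expected number of reactions is calculated.

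**The case against.** The strongest reply is that the risk is small and already handled. Families with a known produce allergy are excluded, and screening goes wider than produce. What remains is a first reaction to ordinary fruit and vegetables, and families have written guidance for it. Club staff hand over boxes at pickup each week, so there is regular contact. Consent pages and handouts are not in the text available here and may give a contact for problems. No safety hypothesis is planned, and no estimate, test or power figure depends on this.

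Most of that stands, and it rules out several stronger readings that a reader might infer.

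- *That the withdrawal criterion cannot operate, or that reactions must go uncounted.* Section 35 does not restrict where the information comes from, and a spontaneous report can trigger it. The supportable statement is that it depends on such reports.
- *That section 35 contradicts itself* by providing for withdrawal on safety grounds and then saying "There are no procedures in place to ensure the safety of a participant that is withdrawn early". The first part concerns continuing in the program and the second the act of leaving it. The two are compatible.
- *That the goal sheets extend new-food exposure to about week 15.* This follows only from the section 4 description. On the section 11 description the sheets concern foods already supplied. They are optional on either description, and no boxes are scheduled after week 4.
- *That the blank data safety monitoring details in section 34 are an omission.* The form allows that section to be skipped when there is no monitoring plan or board.

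The reply does not supply a question about reactions. Handing over a box is not described as including one, and guidance to families is not data collection.

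**Conclusion.** The concern holds in a limited form. The protocol names new food allergy or sensitivity as an intervention-arm risk and screens for known allergy, but describes no structured capture of reactions at any time after randomization. The section 35 criterion can be applied, though only on unsolicited reports. Any count of reactions would be unreliable, and a count of zero would be uninformative. With active questioning and complete response, a zero count would exclude per-child rates above about 3.9% (75 children) to 2.1% (140 children), one-sided 95%.

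This rests on the instruments and forms as the protocol describes them. The full questionnaires, handouts and consent text were not available and might contain a reporting contact or a relevant item. The point affects harms information and leaves the primary analysis unchanged. It is a cheap improvement, not a flaw that threatens the trial's main conclusion.

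**What to change.** 1. Add one question on whether the child or caregiver had a reaction to a program food to the recipe text in weeks 1 to 4 and to each of the five goal sheets. Put it in the text message itself, since section 11 allows for families who cannot open the recipe link.
2. Send replies to the unblinded program staff who already check goal sheets, not to the blinded interviewers or the blinded principal investigator. Do not add the item to the mid-point interview: an interviewer who learns the arm there may later take the end-point diet data.
3. Log week, food and outcome for each report. Record non-response separately so that silence is not counted as zero.
4. State which unblinded role receives reports and who applies the existing section 35 criterion. Timing, follow-up and the content of that criterion are for the investigators.
5. Reconcile sections 4 and 11 on whether the goal sheets ask about new items or items already received.

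The cost is some staff time to monitor replies and an IRB modification; no visits are added. The limitation is that reports would come from the intervention arm only, so they give a rate in that arm and no between-arm comparison.

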Because both the primary and secondary outcome measures are continuous, normally distributed measures, we anticipate having to rely on normal theory analytic methods. Specifically, mixed linear regressions on the primary (HEI) and secondary outcome measures (such as Fruits & Vegetable subscores, BMI and parent HEI) will be fitted to test differential trajectories for two groups from baseline to midpoint and end point assessment of the program, time expressed as days elapsed from baseline. These models readily accommodate differential dropout in the arms with maximum likelihood estimation, random intercepts, and also adjust for any clustering effect of the BGCAA sites. Because randomization will be stratified by whether the family are SNAP recipients or not, the main effect of family's SNAP beneficiary status will be included in all models in addition to the main target terms of interest: two-way interactions of time X treatment, time X SNAP, and their three-way interaction. Overall alpha will be set at 0.05 for each child outcome on these target terms.

In addition to these intention-to-treat (ITT) analyses we will also conduct as-treated (AT) analyses incorporating the 'dose' variable that will be formed based on implementation database elements that permits the tracking of program elements consumed/ picked up/ attended by the target child and his/her parent/guardian in the two active arms. In AT models, total dose taken-up by the end of the program will enter into product terms with time. As is typical, we expect the AT models to have greater sensitivity/ precision in estimating the added value of the family support beyond the elements of the after-school program with CATCH for change in HEI and secondary outcomes. In addition the dose variable sheds light on the effects of Boys and Girls Club programming, including CATCH, regardless of other incentives. Statistical controls for family demographic characteristics, food insecurity, child age, sex, and SNAP beneficiary status will be included in the AT framework as 'dose' is not completely controlled by the randomization and hence would be expected to be correlated with these characteristics (e.g. economically disadvantaged families may be more likely to uptake more of the program elements).

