- a. Interested participants will be called by study staff to screen and share consent and assent information, which is expected to last approximately 15 minutes. Consent and assent will be collected verbally in order to reduce burden on participating families.
- b. After RA obtains consent and assent, if time allows, will also gather baseline data over the phone on the same phone call. If time constraints exist, staff will schedule another time and date for baseline phone measurements (more below).

3. Participating families (parent-child dyads) will then be allocated to study arms as follows:

- a. Dyads with one reference caregiver and one reference child in the BGCAA after-school program will be randomized to one of the two active arms (family support + after-school program, or after-school program only)

Measurements and data collection procedures:

There will be 3 data collection measurements over the course of 19 weeks. These are the baseline, mid-, and end-point measurements. The initial baseline phone call will take approximately an hour (counting consent/assent), while the mid- and end-point measurements will take approximately 45 minutes to an hour. The height and weight measurements will take an additional 5 minutes. In total, participants can expect to spend approximately 4 hours of their time on study-related measurements and data collection.

Data will be collected by members of study staff listed as study team members in UT-RMS. Data collection will only happen with the families that are actively participating and have consented in to the research, not the families participating in BGCAA's regular program and not participating in our research study.

Questionnaire data:

At each measurement, the research associate (RA), blinded to the active study arm of the participants, will gather parent-reported data and child-reported data with parental guidance over the phone as structured interviews. The structured interviews will be done as follows:

1. The RA places the phone call to the reference parent/caregiver.
2. After introducing themselves and the purpose of the call, they will proceed with the questionnaires as shown in Section #4 (e.g., diet, physical activity, demographics). Questionnaires for children will be asked to the parent (guardian-reported) who can confirm answers with the child if they are present and as needed. At the parent's discretion, the child may answer the questions themselves.

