 - With n=113 households in each active arm, we can detect a moderate effect size $d = .45$.
 - Considering 15% attrition in each arm, we would end the study with n=96 in each active arm and able to detect an effect size of $d = .49$.
- If we successfully enroll 50%, N=150
 - With n=75 in each active arm, we can detect a difference of moderate effect size $d = .55$.
 - Considering 15% attrition, n=64 in each arm enable us to detect an effect size of $d = .60$.

Therefore, we will invite to participate in the study all households with at least one eligible child to maximize our ability to detect meaningful mean differences in children's HEI between the two active arms.

SCREENING AND RECRUITMENT

16

Identification and Screening

*Check the box below if this study involves a screening process **prior** to the informed consent process.*

This study involves obtaining information or biospecimens for the purpose of screening, recruiting or determining eligibility of prospective subjects prior to informed consent by either:

- 1. Oral or written communication with the prospective subject or LAR**
- 2. By accessing records containing identifiable private information or stored identifiable biospecimens.**

17

Identification and/or Screening Procedures

Describe the identification and/or screening procedures below.

The Identification of interested families will be done both by the BGCAA staff and our study staff through the various places where BGCAA can be reached, as follows:

- Distribution of flyers containing a QR code that links to an interest form to request more information later – at BGCAA sites & digitally via Class Dojo app that BGCAA staff use to communicate with families. In this form, if collecting interest information, we will collect the parent/guardian name, child name, school and/or afterschool site they attend, contact phone number, grade child will be in the fall, and preferred language. The path the QR code takes

them will be to a secure and HIPAA-compliant database (UT Box, REDCap, and/or UT Qualtrics) that will securely house the information to be filled out by the parent/guardian.

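### Section 35 allows a randomised family to be removed from the study when the child leaves BGCAA, so phone-collected diet outcomes may be lost from an analysis labelled ITT

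*Combined protocol and SAP*

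**What the plan says.** Section 35, prompt A, asks the investigator to "List the criteria for withdrawing individual participants from the study". The answer gives two grounds. One is safety, which is not at issue here. The other reads: "They may also be removed if a child leaves the BGCAA program and is in one of the randomized arms".

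Section 5 labels the main comparison ITT: "In addition to these intention-to-treat (ITT) analyses we will also conduct as-treated (AT) analyses". Its provision for missing outcomes is the mixed model: "These models readily accommodate differential dropout in the arms with maximum likelihood estimation".

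The outcome table in Section 4 gives the mode of collection for the child's diet as "Guardian-reported Structured interview over the phone by RA". Section 11 (Questionnaire data) confirms that the research associate "will gather parent-reported data and child-reported data with parental guidance over the phone as structured interviews". In Section 11 only height and weight depend on being at the site, through the field day.

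Section 11 also limits measurement: "Data collection will only happen with the families that are actively participating and have consented in to the research". In context this separates study families from other BGCAA families. It does not settle whether a randomised family whose child has left is still called.

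**The concern.** Leaving BGCAA happens after randomisation and is a form of non-adherence. An ITT comparison keeps such families in their assigned arm and measures them where it can. Here it can, because the interview is a phone call to the guardian. If leavers are removed from the study, their mid-point and end-point diet scores are missing because of a study rule and not because they could not be obtained.

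Likelihood estimation handles this only if dropout is missing at random given what the model contains: time, arm, SNAP status, their interactions, site and earlier outcomes. Section 5 itself expects attendance among after-school-only participants to follow parental employment, income, siblings and other caretakers. It adds family characteristics only to the as-treated models. If those factors also drive leaving and diet change, the assumption fails. No missing-data sensitivity analysis is described.

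At stake are a possible bias of unknown sign in the primary comparison and avoidable loss of sample from a recruitment pool that Section 15 describes as capped by BGCAA capacity.

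**Working it through.** **Plan figures (Section 15).** The 75%-enrolment scenario starts with 113 per arm. With 15% attrition, 113 × 0.85 = 96.05, which matches "Considering 15% attrition in each arm, we would end the study with n=96 in each active arm". That is 113 − 96 = 17 lost per arm, 34 in all. The recruitment target also reproduces: 120 / 0.85 = 141, against approximately 140.

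**Inflation implied by the detectable effects.** With two-sided α = .05 (sidedness is not stated, so this is assumed) and 80% power, the multiplier is 1.9600 + 0.8416 = 2.8016. The implied variance inflation is n d² / (2 × 2.8016²):

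| n per arm | d | implied inflation |
|---|---|---|
| 113 | .45 | 1.458 |
| 96 | .49 | 1.468 |
| 75 | .55 | 1.445 |
| 64 | .60 | 1.468 |
| 120 | .47 | 1.689 |

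The four scenario rows agree at about 1.455. The 120-per-arm row does not, so both bases are shown below.

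**Precision.** Detectable effect = 2.8016 × √(2 × inflation / n). Power for d = .47 is Φ(.47 / √(2 × inflation / n) − 1.96).

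| inflation | n per arm | detectable effect | power for .47 |
|---|---|---|---|
| 1.455 | 96 | .488 | .770 |
| 1.455 | 113 | .450 | .834 |
| 1.69 | 96 | .526 | .707 |
| 1.69 | 113 | .485 | .776 |

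The n = 113 rows are upper bounds. They apply only if every lost family is a BGCAA leaver and every one is still interviewed.

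**Bias.** The documents give no leaving rate and no outcome difference for leavers, so these are assumed cases. The model is outcome on arm, time and arm × time with a random intercept, fitted by generalised least squares to expected values. Outcome SD is 1 and within-child correlation is .3, .5 or .7. Waves are at 0, .35 and 1 of follow-up (the mid-point is weeks 5–8 of about 19). Leavers are lost before either the mid-point or the end-point. The estimand is the arm difference in change by the end-point, with all randomised families followed. Removal is applied to every leaver.

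| Case | Full follow-up | With removal | Bias |
|---|---|---|---|
| (a) 10% leave each arm; intervention leavers gain 0, stayers .47 | .423 | .465 to .470 | +.042 to +.047 |
| (a) 15% leave each arm, same | .400 | .463 to .470 | +.063 to +.070 |
| (a) 10% leave each arm; leavers keep half the gain | .446 | .468 to .470 | +.021 to +.024 |
| (a) 15% leave each arm; leavers keep half the gain | .435 | .466 to .470 | +.032 to +.035 |
| (a) Leavers gain as much as stayers | .470 | .470 | 0 |
| (b) 10% intervention v 20% control leave; leavers drift 0.5 SD lower for unmodelled reasons | .520 | .470 to .476 | −.050 to −.044 |
| (c) As (b), but the 0.5 SD gap is already present at baseline | .470 | .438 to .461 | −.032 to −.009 |
| 15% leave each arm, same 0.5 SD drift in both | .470 | .470 | 0 |

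The full-follow-up values in (a) are simple averages: .47 × .90 = .423 and .47 × .85 = .400. In (b) the value is .47 + 0.5 × (.20 − .10) = .520. Case (a) shows that bias does not need unequal leaving: with equal rates, removal moves the estimate toward the effect among children who stay. In (c) the model recovers part of the gap from the baseline score, so the bias is smaller than in (b).

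**The case against.** The strongest reply is that this is a permissive line in an ethics form, not an analysis-set definition. Removal is discretionary and applies to both arms. Visits made before removal can stay in the mixed model, the plan names differential dropout, and it allows for 15% attrition. The form asks for the withdrawal terms to appear in the consent form, which is not available here and may say more.

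The bias cases can also be called unfavourable. Produce boxes come only in weeks 1–4, and Section 3 reports pilot gains sustained at 8 weeks, so a child leaving after week 4 could keep part of the benefit. Keeping half the gain halves the bias in (a). No text supports control families leaving at twice the intervention rate. Even .07 SD is small beside detectable effects of .45 to .60. One added sentence on continued calls might be enough, without deleting the ground.

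Much of this stands as a limit on size: the event rate is unknown, the bias can be zero, and the larger cases treat a discretionary rule as always applied. It does not remove the gap. No criterion says when the discretion is used, and no available text keeps leavers in follow-up. The attrition allowance protects power, not validity, and likelihood estimation cannot verify its own missing-at-random assumption.

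**Conclusion.** The concern holds. Section 35 permits ending follow-up of a randomised family for an adherence event that does not prevent measurement of the primary diet outcomes, and no other section says the calls continue. The effect on the estimate is probably modest: from zero up to about +.07 SD or −.05 SD in the cases examined, with the sign unknown. These rest on assumed leaving rates of 10–20%, assumed outcome differences, and removal of every leaver.

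The most that could be regained in the 75%-enrolment scenario is a detectable effect of .45 instead of .49. Power for .47 would be 83% instead of 77% on the scenario-row inflation, or 78% instead of 71% on the 120-per-arm basis. The change should be made because it is cheap and because outcomes not collected during follow-up cannot be recovered afterwards. Confidence is medium, since how often the rule would be used is not known.

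**What to change.** In Section 35, delete leaving BGCAA as a ground for removal from the study and leave the safety ground unchanged. State that a household whose child leaves is still called for the mid-point and end-point interviews and is analysed in its randomised arm, unless consent is withdrawn or contact is lost. Deletion is cleaner than an added sentence, because the prompt concerns withdrawal from the study itself. Align Sections 5 and 11 so that the wording on active participation cannot be read as excluding leavers. Record the leaving date for the dose analyses and report leaving by arm. This concerns outcome follow-up only; whether support items continue after leaving is for the sponsor to state.

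Section 45 pays $30 per measurement, so two further interviews cost at most $60 per leaver. If all 34 families lost in the 75% scenario were leavers with neither interview done, that is 34 × $60 = $2,040. At 45–60 minutes per interview (Section 11), staff time is at most 34 × 2 × 0.75 to 1 hour, or 51 to 68 hours, plus tracing. Control families are due $120 in gift cards at study end. The documents do not say whether a removed family would forfeit this; if so, keeping 17 controls adds up to 17 × $120 = $2,040. Field-day height and weight may still be missing for these children.
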